Efficacy data from Phase I and II studies in melanoma suggest a trend of increasing durability and progression free survival (PFS) rates with increasing doses and duration of exposure to ipilimumab. However, preliminary data suggests that 10mg/kg of ipilimumab is associated with a higher frequency of SAEs and serious (Grade 3 or higher) irAEs than 3mg/kg of ipilimumab(2, 11, 12). It appears that an increased awareness and better management of these side effects has led to a decrease in their severity and an improvement in their control in recent trials. We propose to use ipilimumab at 3 mg/kg dose administered as 4 doses every 3 weeks and will implement a tight safety rule (see section 7.3) to stop the trial in case of excess toxicity.

It is important to note that because ipilimumab works indirectly through stimulation of the immune system by enhancing T-cell activation, its effect on tumor burden may take weeks to months to become apparent. The clinical activity of ipilimumab may manifest, not only as an early objective response, but also as stable disease (SD) with slow, continuous decline of tumor burden toward response and, in some cases, as a late objective response after initial tumor volume increase (12). For example, in one study (MDX010-19) the time to first response ranged from day 40 to day 441 (10). Durable responses and SD after treatment with ipilimumab have been observed in several malignancies, including melanoma, prostate and renal cell carcinoma.

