Preliminary safety data on ipilimumab and SBRT: Combining ipilimumab and SBRT was safe with signs of efficacy (1, 25). In this phase I trial, treatments combining liver or lung SBRT at 50 Gy in 4 fractions or 60 Gy in 10 fractions concurrently or sequentially with ipilimumab at 3 mg/kg for 4 doses were considered safe. Two patients (6%) had DLTs, and even though rates of grade 3 treatment-related toxicity were 34% of treated patients, most were self-limiting and managed as an outpatient. Data on efficacy is encouraging, with 10% out-of-field irPR and 23% clinical benefit. Though these data are encouraging, the outcome may be improved by adding another I-O agent to the treatment regimen: we propose to test the safety and efficacy of combining BMS-986156 with ipilimumab + SBRT. However, there are no clinical data available on the safety of BMS-986156 + Ipilimumab. Treatment group 1 will be initiated to determine the safety of combining BMS-986156 (30 or 100 mg) and ipilimumab (3 mg/kg). After BMS-986156 dose determination in group 1, group 2 will be initiated with BMS-986156 (dose as determined in group 1) and ipilimumab plus SBRT. Recently, in our preclinical model of PD-1 resistance we have shown a dramatic improvement in radiation-induced abscopal responses with the addition of anti-GITR antibody. Moreover, an ongoing study (CA009-002) has recently provided human safety data following administration of a flat dose of nivolumab, another checkpoint inhibitor, in combination with BMS-986156, an anti-GITR monoclonal antibody (26). Altogether, these studies suggest that anti-GITR, a T-cell agonist, may potentiate a T cell mediated response and may contribute to abscopal responses observed when SBRT is administered with checkpoint inhibitors such as ipilimumab or nivolumab. These findings likewise prompted us to include additional arms involving concurrent SBRT administration with anti-GITR plus either ipilimumab or nivolumab in this study. Treatment group 3 will be initiated with nivolumab (480mg) plus BMS-986156 (30mg) and SBRT combination therapy.

Our hypotheses are as follows:

1) SBRT targeting a limited number of liver or lung metastasis in conjunction with ipilimumab and BMS-986156 or nivolumab and BMS-986156 combination therapy will result in improved local and systemic disease control.

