7.1.1.1 Group 1: Dose Escalation of BMS-986156 when combined with ipilimumab

Treatment group 1: A modified 3+3 dose escalation then expansion to a total of 10 patients per arm (escalation + expansion, if applicable) will be performed on two dose levels of this combination therapy.

- The first 3 subjects will be enrolled at dose level 1 (3 mg/kg ipilimumab + 30 mg BMS-986156).
 - If 0 out of these 3 patients have a DLT, 3 patients will then be enrolled on dose level 2 (3 mg/kg ipilimumab + 100 mg BMS-986156).
 - If 1 of 3 subjects have a DLT in dose level 1 (30 mg), 3 more patients will then be enrolled at this dose level. If only 1 of the 6 total subjects at dose level 1 has a DLT, then 3 patients will then be enrolled on dose level 2, 100 mg BMS-986156.
 - Additionally, 4 patients will be enrolled on dose level 1 to a total of 10 patients at 30 mg BMS-986156.
 - If 2 of 3 subjects have a DLT at dose level 1, then dose escalation is stopped and the MTD is reached (dose level 1).
- Subjects will be receiving 3 mg/kg ipilimumab + 100 mg BMS-986156 at dose level 2.

- At this dose level, if 0 of the 3 subjects have a DLT, then both dose level 1 and dose level 2 will be expanded to more patients so that each arm has a total of 10 patients enrolled.
- If 1 of the 3 subjects at dose level 2 have a DLT, 3 more subjects will then be enrolled at this dose level. If only 1 of the 6 total subjects at dose level 2 have a DLT, both dose level 1 and dose level 2 will be expanded to more patients so that each arm has a total of 10 patients enrolled. If 2 of the 6 total subjects at dose level 2 have a DLT, then dose escalation is stopped and the MTD is reached (dose level 1). Only dose level 1 will be expanded to a total of 10 patients enrolled.
- If 2 of 3 subjects at dose level 2 have a DLT, then dose escalation is stopped and the MTD is reached (dose level 2).
- The expansion phase dose will be selected based on safety and response readouts. For example, the dose exhibiting the best therapeutic response or pharmacodynamic profile with the best safety profile.

Dose Escalation of BMS-986156 when combining with Ipilimumab.

Dose Level 1 3 mg/kg Ipilimumab + 30 mg BMS-986156

Dose Level 2 3 mg/kg Ipilimumab + 100 mg BMS-986156

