7.1.1.2 Group 2: Dose De-Escalation of BMS-986156 when combined with ipilimumab plus SBRT

BMS-986156 dose as determined in group 1, for combination treatment with ipilimumab, before adding SBRT to the treatment regimen.

Treatment group 2: A modified 3+3 dose de-escalation then expansion to a total of 20 patients will occur at the MTD.

The first 3 subjects will be enrolled at dose level 1 (3 mg/kg ipilimumab + BMS-986156).

- If 0 out of these 3 patients have a DLT, 3 additional patients will then be enrolled on this same dose level.
- If 1 of 3 subjects have a DLT, 3 more patients will then be enrolled at this dose level. If only 1 of the 6 total subjects at dose level has a DLT, then this dose level will be considered safe and all other patient in this arm will be treated at this dose level.
- If 2 of 6 subject have DLT at dose level 1, then the dose will be de-escalated as per table below.
- If 2 of 3 subjects have a DLT at dose level 1, then the dose will be de-escalated as per table below

Dose De-Escalation of Ipilimumab when combining with BMS-986156 plus SBRT.

If MTD from group 1 finds the 30mg BMS-986156 then:

Dose Level 1 3 mg/kg Ipilimumab + 30 mg BMS-986156

Dose Level -1 1 mg/kg Ipilimumab + 30 mg BMS-986156

If MTD from group 1 finds the 100mg BMS-986156 then:

Dose Level 1	3 mg/kg Ipilimumab + 100 mg BMS-986156
Dose Level -1	1 mg/kg Ipilimumab + 100 mg BMS-986156
Dose Level -2	1 mg/kg Ipilimumab + 30 mg BMS-986156

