- Any clinically ≥ grade 3 non-hematologic toxicity as defined in the NCI CTC v4.0, expected and believed to be related to the combination of study drug and radiation (except nausea and vomiting, diarrhea and electrolyte imbalances responsive to appropriate regimens, alopecia or fatigue lasting less than 7 days).
- Grade 3 Febrile neutropenia
- Any grade 4 neutropenia (with or without fever and/or sepsis) or thrombocytopenia (without bleeding) lasting at least 1 week or longer (as defined by the NCI-CTC v4.0).
- Any of the Grade 4 hematologic adverse events for >7 days.
- Any ≥ grade 3 nausea or vomiting lasting > 5 days despite anti-emetics regimens or ≥ grade 3 diarrhea refractory to anti-diarrhea medications, >48 h.
- Any Grade 2 drug-related uveitis or eye pain or blurred vision that does not respond to topical therapy and does not improve to Grade 1 severity ≤2 weeks OR requires systemic treatment. Any other grade 3 non-hematologic toxicity including symptoms/signs of vascular leak or cytokine release syndrome; or any severe or life-threatening complication or abnormality not defined in the NCI-CTCAE v4.0 that is attributable to the therapy, with the following EXCEPTIONS:
 - Grade 3 or grade 4 electrolyte abnormalities that are not complicated by associated clinical adverse experiences, last ≤48 hours and either resolve spontaneously or respond to conventional medical intervention
 - Isolated Grade 3 elevation of amylase or lipase not associated with clinical or radiographic evidence of pancreatitis
 - Isolated Grade 3 fever not associated with hemodynamic compromise (eg, hypotension, clinical or laboratory evidence of impaired end-organ perfusion)

- Grade 3 endocrinopathy that is well controlled by hormone replacement
- Grade 3 tumor flare (defined as pain, irritation, or rash that localizes to sites of known or suspected tumor)
- Grade 3 fatigue for ≤ 7 days.
-

Group 2 and Group 3 definition of DLTs:

- DLTs used to define the MTD in combination with radiation section 7.1.1.2 and 7.1.1.3 will only use DLTs associated with organ toxicity for the organ irradiated.
- SBRT related adverse events: Any grade ≥ 3 events occurring in radiation volume field will be considered as DLT.
- Any \geq Grade 3 bronchospasm or other hypersensitivity reactions lasting for > 6 h;

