The Principal Investigator shall obtain all such permissions and authorizations as may be necessary or desirable to allow the collection and use of information protected under federal privacy laws and state privacy laws, including permission/authorization for monitoring and analysis (including re-analysis in combination with results of other studies), for regulatory submission purposes and for applicable reporting (if any).

Tumor response will be determined using the Immune Related Response Criteria (irRC) as described in section 8.3.

The Investigator is responsible for completing an efficacy/safety summary report, and submitting it to the IND Office Medical Affairs and Safety Group, for review and approval. This should be submitted after the first 3 evaluable patients in groups 1 and 3 complete 29 days of study treatment, and after the first 3 evaluable patients in group 2 complete 43 days of therapy initiation, and every 3 evaluable patients per group thereafter. IND Office approval must be obtained prior to advancing/changing dose levels.

A copy of the cohort summary should be placed in the Investigator's Regulatory Binder.

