10.1. Data Set Descriptions

For group 1, after BMS-986156, dose as determined in group 1, an additional 4 patient expansion per dose level (10 patients total for each dose level) will be enrolled in that group, at the determined dose from group 1, to help determine biological endpoints. Should DLTs occur in more than 33% of patients enrolled into this expanded group, dosing at that level will be stopped. The next lower dose level will be considered the safe dose. A review of all DLTs observed will be conducted, and the need to lower the dose will be based on the discussion and agreement between the IRB and the Investigator.

All patients who receive any ipilimumab, BMS-986156, or nivolumab will be considered evaluable for toxicity.

For toxicity and response: all patients receiving at least 1 (concurrent group) or 2 (sequential group) treatment with trial drugs and completed half of the planned radiation treatment (except for group 1 where no radiation is given) will be considered evaluable for toxicity and response and included in the efficacy data set.

Group 1: (Total of 20 patients: 10 patients with 30 mg and 10 patients with 100 mg of BMS-986156, when combined with ipilimumab at 3mg/kg). Nivolumab (480mg) Q4W monotherapy will be administer for 26 cycles.

Group 2: 20 patients: trial drugs, two doses of ipilimumab (3mg/kg) combined with BMS-986156 (dose as determined in group 1) are given before SBRT. SBRT is given sequentially; followed by 2 more doses of ipilimumab + BMS-986156. Nivolumab (480mg) Q4W monotherapy will be administer for 26 cycles.

Group 3: 20 patients: First dose of trial drugs nivolumab (480 mg) and BMS-986156 (30 mg) are given concurrently with SBRT; followed by 3 doses of nivolumab (480 mg) and BMS-986156 (30 mg). Finally, Nivolumab as monotherapy for 22 cycles. Nivolumab will be administered for a total of 26 cycles in this group.

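### The trial-stopping safety rule that section 3.1.1 places in section 7.3 is not there, and no stated DLT count stops dosing in the group 2 expansion after its first six patients

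*Combined protocol and SAP*

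**What the plan says.** Section 3.1.1, explaining the choice of ipilimumab 3 mg/kg, says the investigators "will implement a tight safety rule (see section 7.3) to stop the trial in case of excess toxicity". Section 7.3 covers duration of therapy, delay, restart, permanent discontinuation and removal from study. Every criterion there acts on one patient.

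The group-level safeguards sit elsewhere:

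- **Section 7.1.1.2 (group 2).** Two DLTs in 3 or in 6 patients lead to de-escalation. With only 1 in 6, "then this dose level will be considered safe and all other patient in this arm will be treated at this dose level". The group is then filled to 20.
- **Section 7.1.1.3 (group 3).** The same rule.
- **Section 10.1.** "Should DLTs occur in more than 33% of patients enrolled into this expanded group, dosing at that level will be stopped". The paragraph opens by naming group 1 and describes that group's expansion of 4 patients per dose level.
- **Section 10.** The investigator sends a summary report to the IND Office for review and approval after the first 3 evaluable patients "and every 3 evaluable patients per group thereafter". No threshold is given. The explicit requirement for approval concerns advancing or changing a dose level.
- **Sections 9.1 and 9.2.** SAEs go to the IND Office within 5 working days and to the drug manufacturer within 24 hours or one business day.

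Section 7.2.1 says that the DLTs used to define the MTD in groups 2 and 3 "will only use DLTs associated with organ toxicity for the organ irradiated". It then lists systemic events as DLTs for those same groups.

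**The concern.** Safety is the primary objective, and section 3.3 states that "there are no clinical data available on the safety of BMS-986156 + Ipilimumab". Group 1 tests the pair without SBRT, so group 2 is the first use of the three together. The plan sets a numeric limit for a 4-patient expansion in group 1 but none for a 14-patient expansion that adds radiation. Whoever reads the three-patient reports has no agreed limit, although section 3.1.1 says one exists.

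It is also unclear what would be counted. If only toxicity of the irradiated organ counts, colitis or hypophysitis after lung SBRT would not, and those are the ipilimumab toxicities that prompted the promise. Timing adds to this. Section 5.1.9 gives a median onset of 7 to 9 weeks (49 to 63 days) for grade 3-5 immune-related events with ipilimumab, whereas the group 2 DLT window closes at day 43.

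**Working it through.** The plan gives no target DLT rate and no operating characteristics, so there is no figure of its own to reproduce.

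**Inputs from the documents.** Gate of at most 1 DLT in 6 and group size 20 (7.1.1.2); limit of more than 33% (10.1); reviews every 3 patients, hence at 9, 12, 15 and 18 (section 10); 43-day window (7.2); 3 patients per month (10.2.5).

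**Assumption.** The true DLT rate p is unknown. The nearest figures come from the earlier ipilimumab plus SBRT trial (3.3): "Two patients (6%) had DLTs, and even though rates of grade 3 treatment-related toxicity were 34% of treated patients". The 34% is not a DLT rate and its time window is not stated. I use 6% to 40%.

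**Step 1: passing six patients.** P(pass) = (1-p)^6 + 6p(1-p)^5. At p = 0.34 this is 0.083 + 0.255 = 0.338.

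**Step 2: further DLTs under the current text.** 14p among groups that pass; at 0.34, 14 x 0.34 = 4.76. No count is triggered.

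**Step 3: extending the 33% rule.** Read literally (above 0.33), the cumulative limits are 3/9, 4/12, 5/15 and 6/18. Read as more than one third, they are 4/9, 5/12, 6/15 and 7/18. The chance of crossing comes from an exact recursion starting from 0 or 1 DLT in six.

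Example, p = 0.34, literal reading, first look. Given a pass, 1 DLT has probability 0.255/0.338 = 0.756 and 0 DLTs 0.244. P(at least 2 of 3) = 0.268 and P(3 of 3) = 0.039. So P(stop at 9) = 0.756 x 0.268 + 0.244 x 0.039 = 0.212. The later looks add 0.118, 0.078 and 0.057, total 0.465.

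**Step 4: DLTs avoided.** Sum over looks of P(stop at n) x p x (20 - n - k, not below 0), where k patients enter while a decision is pending. At 0.34 with k = 0: 0.34 x (0.212 x 11 + 0.118 x 8 + 0.078 x 5 + 0.057 x 2) = 1.29 given a pass; 0.338 x 1.29 = 0.43 over all groups. For overrun I take k = 4, from 43/30.4 x 3 = 4.2, which supposes that all accrual goes to group 2.

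| True rate | Pass six | Further DLTs if passed, no rule | Stop given pass: literal / one-third | Stop, all groups: literal / one-third | DLTs avoided per group, waiting: literal / one-third | DLTs avoided, literal, overrun of 4 |
|---|---|---|---|---|---|---|
| 6% | 95% | 0.8 | 0.4% / <0.1% | 0.4% / <0.1% | <0.01 / <0.01 | <0.01 |
| 20% | 66% | 2.8 | 13% / 3% | 8.3% / 1.7% | 0.14 / 0.02 | 0.08 |
| 30% | 42% | 4.2 | 36% / 13% | 15% / 5.6% | 0.37 / 0.10 | 0.20 |
| 34% | 34% | 4.8 | 47% / 21% | 16% / 7.1% | 0.43 / 0.14 | 0.23 |
| 40% | 23% | 5.6 | 63% / 35% | 15% / 8.2% | 0.48 / 0.20 | 0.26 |

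The figures for all groups multiply by P(pass) and take no account of any screening in group 1.

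**The case against.** **Group 2 is not unwatched.** A reader might infer from section 7.3 that nothing can stop a cohort. The documents do not support that. The 3+3 rules, the group 1 limit, the three-patient reports submitted for approval and SAE reporting all exist, and the IND Office could intervene on judgement. This stands. What is missing is a limit agreed in advance. SAE reporting is also a partial backstop only: under section 9.1, admission for high-dose intravenous steroids is not an SAE unless the event has failed to improve within 7 days.

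**The six-patient gate and group 1 already filter bad doses.** Largely true. At 34%, one group 1 dose level meets the 0/3 or 1/6 criterion with probability 0.66^3 + 3 x 0.34 x 0.66^5 = 0.42, so the table overstates how often a dose that toxic reaches group 2. The filter has holes, though. Section 1 lets group 2 open with up to 2 DLTs in 6, and treats 3 or more in 6 as a delay until 10 patients have been treated, not a bar. Section 7.1.1.1 reads "If 2 of the 6 total subjects at dose level 2 have a DLT, then dose escalation is stopped and the MTD is reached" and falls back to dose level 1, yet with 2 DLTs in 3 at dose level 2 it names dose level 2 as the MTD. It gives no outcome for 2 in 6 at dose level 1.

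**The organ-only reading looks alarming.** If the gate counted only irradiated-organ events at 6% while all listed events occurred in 34%, 95% of groups would pass and then expect 4.8 further listed events. This is illustration only. The 6% is reported simply as DLTs, not as organ toxicity, and the 34% is not a rate of listed events.

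**Conclusion.** The cross-reference in section 3.1.1 is wrong, and no stated DLT count stops dosing for group 2 patients 7 to 20. What counts as a DLT for the MTD decision in groups 2 and 3 is ambiguous. Group 3 has the same gap, as a secondary point: the promise concerns ipilimumab, which group 3 does not receive.

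The effect of a rule is modest. At assumed rates of 30% to 40%, the literal reading stops about 15% of all groups and avoids 0.37 to 0.48 DLTs per group with waiting, or 0.20 to 0.26 with a 4-patient overrun. The one-third reading avoids 0.10 to 0.20 with waiting. At the 6% DLT rate of the earlier trial the effect is almost nil. A reader might infer that large excess harm is likely; the documents give no DLT rate for this combination, so they support no such claim. The case rests on a missing rule that the protocol says is present, in an untested combination, and on how little it takes to supply one. It should be fixed.

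**What to change.** 1. In section 3.1.1, point to sections 7.1.1 and 10.1 instead of 7.3.
2. In section 10.1, extend the existing 33% rule to group 2, preferably also group 3, applied cumulatively at the three-patient reviews. Write it as integer counts: 3/9, 4/12, 5/15, 6/18 if 33% is meant literally, or 4/9, 5/12, 6/15, 7/18 if more than one third is meant. The literal counts fit better with a gate that de-escalates at 2/6. State the action on crossing (pause, then de-escalate or stop).
3. In section 7.2.1, state that the count takes all events on the group 2/3 DLT list, including systemic immune-related events, and whether the six-patient gate uses the same count.
4. State whether events starting after day 43 count, and whether enrolment waits for the window to close.
5. Report the operating characteristics of the chosen boundary.

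This is protocol wording and a short table, with no new visits or reviews. The costs are possible false stops and time. Given six passed, the literal rule stops 13% of groups at a true rate of 20% (3% on the one-third reading); the sponsor must say whether 20% would be acceptable. Waiting at all four looks could hold group 2 for up to 4 x 43 = 172 days (group 3: 4 x 29 = 116), longer if later events count and less if other groups enrol meanwhile. Not waiting cuts the benefit roughly in half.

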3.1.2. Anti-GITR Agonistic Antibody (mAb) (BMS-986156)

T-cell costimulation integrates multiple positive and negative costimulatory signals in addition to antigen recognition by the T-cell receptor (TCR). Collectively, these signals govern the balance between T-cell activation and tolerance to antigens. CD28, a member of the immunoglobulin superfamily of costimulatory receptors, provides the second signal in the 2-signal hypothesis of T-cell activation. Other costimulators are members of the tumor necrosis factor receptor (TNFR) superfamily, including GITR (glucocorticoid-induced TNFR-related protein), CD134 (OX40), CD27, and CD137 (4-1BB). Engagement of these receptors by ligand or agonist antibody also potentiates antigen-specific T-cell responses.

GITR is a type I transmembrane costimulatory receptor that is readily detectable on naive murine T cells, with little expression on naive human T cells. GITR expression increases with activation, and its expression on Tregs is higher than on effector T cells. The ligand for GITR is the tumor necrosis factor (TNF) superfamily member GITR-L (TNFSF18). TCR- mediated activation of T cells can be costimulated by GITR engagement, which promotes TCR-dependent cell proliferation along with increased effector functions and reduced apoptosis.

BMS-986156 is an IgG1 agonist antibody that binds to activated human CD4+ and CD8+T cells with EC50's of 0.42-0.44 nM. EC50 values for binding of BMS-986156 to activated cynomolgus T cells (0.86-0.96 nM) were similar to those on human cells, being about 2-fold lower. The affinity of 28F3, the hybridoma parent molecule of BMS-986156, for binding to GITR on activated T cells was 0.7 nM as determined by Scatchard analysis. BMS-986156 is a partial ligand blocker and binds near the N-terminus of the mature GITR protein. BMS-986156 was active in two in vitro functional assays. BMS-986156 potentiated IL-2 release from the murine 3A9 T cell hybridoma upon activation in a dose-dependent manner. BMS-986156 also stimulated IFN- γ release from human CD4+ T cells cocultured with CHO cells stably expressing a single-chain anti-CD3 (OKT3) Fab. While GITR is expressed on activated T cells and on Treg cells, experiments demonstrated that agonism of BMS-986156 reduced the sensitivity of Teff cells to Treg suppression in a co-culture assay. BMS-986156 also elicited anti-tumor activity against an MC38 syngeneic tumor implanted into a mouse where the mouse GITR was replaced with that of human GITR.

BMS-986156 demonstrated ADCC and ADCP activities as well as binding to complement factor C1q in vitro, consistent with an antibody of the IgG1 subclass. As such, BMS-986156 may mediate in vivo ADCC or ADCP and complement fixation of cells expressing GITR. Because levels of GITR are highest among intratumoral Tregs, this subset of T cells is more likely to be depleted which may have a positive consequence for T cell immunity at the tumor site. A high concentration of BMS-986156, in the absence of an anti-T-cell receptor stimulus, elicited no measurable cytokine response from cultured human peripheral blood cells.

GITR is expressed not only in T cells but was also found in a subset of lung tumor cells as determined by IHC. No consequence of GITR engagement by BMS-986156 on proliferation of many GITR+ lung tumor cell lines was observed.

BMS-986156 monotherapy has been evaluated during the dose escalation phase and cohort expansion phase at 10 mg (4 subjects), 30 mg (6 subjects), 100 mg (4 subjects), 240 mg (9 subjects), and 800 mg (11 subjects) of BMS-986156. The majority of the subjects were Caucasian (88.2%) with a median age of 56.5 years. All 34 subjects that have received at least 1 dose of BMS-986156 as monotherapy experienced adverse events (AEs), which were mostly Grade 1 and Grade 2. The most frequently reported AEs (>10% of subjects) were fatigue, nausea, malignant neoplasm progression, constipation, abdominal pain, decreased appetite, pyrexia, back pain, diarrhea, vomiting, dyspnea, headache, peripheral edema, and pain. AEs reported for 20 subjects were considered related to study drug because no other potential cause for the events could be identified. There were no dose-limiting toxicities (DLTs). The 5 most frequent drug-related AEs included pyrexia, nausea, fatigue, chills, and diarrhea.

Overall, the safety profile of BMS-986156 monotherapy is manageable with the MTD not being reached at 800 mg. The safety profile of monotherapy BMS-986156 allowed for dose escalation up to 800 mg. However, monotherapy expansion was discontinued as a result of a decision to develop the drug in combination with nivolumab.

Detailed information about BMS-986156 can be found in the current version of the BMS-986156 Investigator's Brochure (IB) v03.

